## **2. Problem statement**

All surgeries, including laparoscopic surgery, represent a major stressor to the patient with possible sequelae for post-operative well being, including decline in functional capacity, cognitive ability, and even cancer spread. Comorbidities such as diabetes, ischemic heart and vascular disease, stroke, and others have a larger impact on postoperative morbidity and mortality than age (21) (10).

ERAS pathways have been successfully implemented in many surgical specialties, including gastrointestinal, hepato-biliary, pancreatic, urologic, gynecologic, and urologic surgery (22) (23) (24).

The strongest evidence so far has been described in patients undergoing open colorectal procedures (6) (25) (26). Combining minimally invasive laparoscopic surgery and ERAS has been shown to have important clinical and economic benefits and significant reductions in length of hospital stay, but its spread remains slow worldwide.

Implementation of ERAS pathways improves clinical outcomes and induces substantial economic gains (15) (16) (2), and is becoming the optimal strategy for many surgeries when technically feasible (27) (28) (10).

Laparoscopic cholecystectomy can be performed as a day-case procedure with a low rate of complications and admissions/readmissions. Patient acceptance in terms of quality of life variables is similar to that for cholecystectomy with an overnight stay. The day care strategy is associated with a reduction in cost (29).

Laparoscopic cholecystectomy in ERAS program should optimize the surgical outcome and improve a quick recovery and decrease the length of hospital stay. At the University Teaching of Kigali, the current practice is to admit patients for laparoscopic cholecystectomy 24 hours prior to surgery and to discharge most patients within two to three days of surgery with a rate of complications around 5%.

Patients overcrowd CHUK and the hospital bed management is a serious challenge. Patients coming far from their homes and with limited financial resources are suffering to get admitted in hospital for elective and none urgent surgeries like cholecystectomy, We believe that ERP can benefit the hospital with a rapid bed turnover rate, and reduces cost for surgery and hospitalization while providing to the patients with quality care and the same time increasing the comfort of the patient in the post-operative period and minimizing the postoperative complications.

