## **5. Research Methodology**

### **5.1. Methods and Settings**

This is a prospective and cross sectional study. The study will be conducted in Rwanda at the University Teaching Hospital of Kigali from January to December 2021.

Rwanda is a country of 11.9 million in East Africa. There are approximately 80,000 surgical procedures performed annually in Rwanda, 510 major operations per 100,000 populations (30). Rwanda has 4 main referral hospitals performing surgical operations including laparoscopic procedures. The referral hospitals include: University Teaching Hospital (CHUK), University Teaching Hospital of Butare (CHUB), Rwanda Military Hospital (RMH) and King Faisal Hospital, Kigali (KFH, K)

The University Teaching Hospital of Kigali (CHUK) is the major public, tertiary referral and teaching hospital in Rwanda and it is located in the capital in Kigali. It has 565 beds and 11 operating theaters shared among all surgical services. It provides approximately up to 1600 major operative cases in general surgical services every year including 140 cases of laparoscopic surgeries with 75 cases of laparoscopic cholecystectomies. The CHUK started performing laparoscopic surgery routinely long time before others and currently it performs more than 60% of laparoscopic surgeries performed in the Country in different specialties including general surgery, Urology and Gynecology. Considering the above reason, we selected this hospital to represent others and be the site of our research interest.

This study will be conducted in general surgical unit at the University Teaching Hospital of Kigali (CHUK), it has a capacity of 2 operating rooms with 2 lap towers with complete sets of laparoscopic material and around 40 in patient beds.

The population proportion of laparoscopic cholecystectomy is 5% within a total general surgical population size of 1600 patients per year. A range of 50 to 70 patients will allow to have a confidence level of 95% that the real value is within  $\pm 5\%$  of the measured value and have relevant conclusions.

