#### **5.3. Data collection and analysis**

A baseline survey will be conducted to assess the awareness and knowledge of health care professional in charge of perioperative care. From November 2021, we will put in place an ERAS protocol for laparoscopic cholecystectomies. Patients living in Kigali and near Kigali having an easy communication means will be sensitized to adhere to the program.

A multidisciplinary team (Surgeons, Anesthesiologists, nurses, anesthetists and psychologists) will be mobilized to participate in the team. A google sheet questionnaire will be designed to collect information about the awareness and knowledge of perioperative health care professional about ERAS programme and then

a modified ERAS protocol will be put in place and data collection will be done using a coded checklist form and consecutive selection of patients will be done during the study period until we reach at least 50 patients. The operative procedures and instrumentation will be standardized for laparoscopic cholecystectomy, and surgeons who will perform the procedures will be having expertise in laparoscopic cholecystectomy. Reasons for conversion from laparoscopic to open cholecystectomy will be recorded and documented. Emergency patients and patients defined as ASA IV and pediatric patients aged below 16 years will be excluded.

Data will be collected for age, gender, indications for surgery, American Society of Anesthesiology (ASA) class, operative time, adverse events (pain, nausea and vomiting), length of hospitalization, and intra- and post-operative complications. The expenses of surgery and in-hospital care will be calculated and analyzed. On discharge, on day 3 of discharge, day 10, day 15 and day 30 of discharge patient will report outcomes and will be recorded by Surgical Recovery Scale. After discharge, the patients will be called or texted on phone to know about their status and collect information. Data will be recorded using EXCEL. Statistical analysis will be done using SPSS software and the one-way analysis of variance (ANOVA) test, the Chi-square test, and the t Student's test will be used when appropriate for comparisons.

A Univariate analysis will be done to determine variables associated with the length of hospital stay. Pearson's chi square will be calculated to compare variables and..

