## **7. Significance of the study**

The results from this study will determine if ERP can be implemented in our settings and laparoscopic cholecystectomy patients are safe to be discharged on one-day post-operative period in a teaching hospital in Rwanda to increase bed turnover and decrease patients hospital costs.

Recommendations will be formulated to encourage surgeons and hospitals in Rwanda to put in place the ERAS protocols and test it for other surgeries. Finally, this study may posit a direction for related future researches

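### Section 5.3 does not settle whether entry is limited to reachable patients in or near Kigali, while the stay target and the conclusion are worded for all laparoscopic cholecystectomy patients

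*Protocol*

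**What the plan says.** Three statements in protocol section 5.3 bear on who enters.

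- **Who is approached:** "Patients living in Kigali and near Kigali having an easy communication means will be sensitized to adhere to the program". *Near* and *easy* are not defined.
- **How patients are selected:** "consecutive selection of patients will be done during the study period until we reach at least 50 patients".
- **Who is left out:** "Emergency patients and patients defined as ASA IV and pediatric patients aged below 16 years will be excluded". Residence and telephone access are not on this list.

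No sentence connects the first statement with the other two. The variables to be collected (age, gender, indication, ASA class, operative time, adverse events, stay, complications, expenses) do not include residence. Neither do the factors in the regression on length of stay. No log or count of patients not approached is mentioned.

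Other sections speak of a wider population. Section 2 describes the hospital's usual practice and its 72-hour starting point without any residence limit. It counts distant patients among those with the problem: "Patients coming far from their homes and with limited financial resources are suffering to get admitted in hospital for elective and none urgent surgeries". Section 7 says the study will determine whether "laparoscopic cholecystectomy patients are safe to be discharged on one-day post-operative period in a teaching hospital in Rwanda". Section 5.1 adds that "we selected this hospital to represent others and be the site of our research interest".

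**The concern.** Two investigators following section 5.3 in good faith could enrol different cohorts. One would take every elective adult or adolescent case in order of arrival. The other would take only those who live close by and can be telephoned. Both could report a consecutive series.

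The difference matters because the main results are the share discharged by 36 hours, the length of stay and feasibility. Distance from home and ease of contact may plausibly affect when staff and patient are ready for discharge. Section 1 itself says that careful selection of patients is essential for a high success rate.

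With a restricted cohort set against an unrestricted 72-hour starting point, part of any apparent reduction could be case mix. The acceptance rate (objective 5 and the acceptance table in section 6) would also have a different denominator under each reading. With residence unrecorded and no count of patients passed over, the data as planned would not show how far the selection went.

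**Working it through.** **1. The text.** Set side by side:

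| Element | Source | Limit by residence or telephone? |
|---|---|---|
| Patients approached | 5.3 | Yes, though not worded as a criterion |
| Selection rule | 5.3 | No |
| Exclusions (three) | 5.3 | No |
| Data collected, regression factors | 5.3 | Residence absent |
| Usual practice and 72-hour starting point | 2 | No |
| Conclusion | 7 | No |

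The statements can be reconciled if selection is consecutive within a catchment area, but the protocol does not say so.

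**2. Is there a stated figure to reproduce?** None bears on this point. The protocol gives neither the share of patients living outside the Kigali area nor any outcome by residence. The 50 to 70 patients of section 5.1 come from the share of operations that are laparoscopic cholecystectomies and say nothing about selection.

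**3. Form of the bias.** Let *s* be the share of eligible patients outside the area, and let *pN* and *pF* be the 36-hour discharge shares of near and far patients.

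- All-patient share = (1 − *s*)·*pN* + *s*·*pF*
- Overstatement if only near patients enter = *pN* − all-patient share = *s*·(*pN* − *pF*)

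**4. Illustration.** Every input here is an assumption, not a protocol figure: *s* from 20% to 60%, gap from 10 to 30 points.

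- Low end: 0.20 × 10 = 2 points
- Midpoint: 0.40 × 20 = 8 points
- High end: 0.60 × 30 = 18 points

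In the midpoint case with *pN* assumed to be 90% and so *pF* 70%, the all-patient share is 0.60 × 90 + 0.40 × 70 = 82%, against 90% observed. At n = 50 the standard error of 90% is √(0.90 × 0.10 / 50) = 4.2 points, so 8 points is about 8 / 4.2 = 1.9 standard errors.

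**5. Mean stay.** The same form holds, with the gap in hours. If far patients were assumed to stay 6 to 24 hours longer, mean stay would be understated by 0.20 × 6 = 1.2 hours to 0.60 × 24 = 14.4 hours. The reduction aimed at is 72 − 36 = 36 hours.

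**6. What could make the gap small.** The discharge criteria in section 5.2.6 are vital signs, blood results, absence of complications, feeding, passage of gas, mobility and pain control on oral drugs. Section 8.2 says that all patients are discharged on standardised criteria. Distance appears in neither. If the criteria alone govern discharge, the gap may be close to zero, and so may the bias.

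**The case against.** The strongest reply is that the sentence says these patients will be sensitised. It does not say that others are refused. It can be read as outreach, or as a catchment area within which selection is consecutive, which is ordinary usage. Either reading makes the three statements compatible. Distant patients may also gain from beds freed by shorter stays without being enrolled, so a local cohort need not conflict with the rationale in section 2. Section 7 states what the study hopes to determine and is not a reported conclusion.

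Much of this stands. A reader might infer that the protocol admits only Kigali patients; the word *only* is not there, and the restriction is an inference. It remains the natural reading, because no other sentence says who is approached. If it was not meant, the text still needs correcting. The catchment reading does not rescue the wording of section 7 or the 72-hour comparison, since neither is limited to that catchment.

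Two further inferences are tempting and not supported:

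- **Readmission.** A reader might assume that a local cohort also flatters the readmission rate. Patients living nearby may be more likely to return to this hospital when a problem arises, so the direction is uncertain and may be reversed.
- **A large central bias.** Taking 40% outside with a 30-point gap gives 0.40 × 30 = 12 points, but 30 points is the top of the assumed range. The midpoint gives 8 points, and the clinical discharge criteria leave room for much less.

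**Conclusion.** The point holds as an inconsistency about who enters, with a consequence for what the study can conclude. Section 5.3 names nearby, reachable patients as those to be approached and then describes a consecutive series whose exclusions omit both conditions. The stay target and the conclusion are worded without that limit. Only the protocol is at hand and an SAP may exist, but eligibility belongs in the protocol.

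If the restriction applies, early-discharge share, mean stay and feasibility may look better than for all patients. The size cannot be computed from the protocol. The 2 to 18 points, with 8 at the midpoint, and the hours given for mean stay rest wholly on assumed shares and gaps. They show that the effect could matter, not that it does. No direction is claimed for readmission.

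**What to change.** State in section 5.3 whether residence and telephone reachability are eligibility criteria.

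**If they are:**
- Define them, and describe the series as consecutive patients meeting these criteria.
- Add residence to the data collected.
- From the theatre list, count the elective laparoscopic cholecystectomies in the period that were not approached, with the reason.
- Limit the conclusion in section 7 and the comparison with the 72-hour stay to patients living near the hospital and reachable by telephone.

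**If they are not:** delete the restriction and approach all eligible patients consecutively.

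The stay of patients outside the programme should not be used as evidence of selection bias. They did not receive the ERAS pathway, so any difference would mix residence with pathway.

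The cost is an edit to sections 5.3 and 7, one added variable, and a short count from routine lists (about 75 laparoscopic cholecystectomies a year by section 5.1). If the restriction is kept, the price is a narrower conclusion. Nothing here changes the discharge criteria or the care given.

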The aim of our study is to assess the feasibility and safety of laparoscopic cholecystectomy in the ERP by decreasing the length of stay from 72 hours to 36 hours, hospital bed turnover and evaluate the adverse events and cost related in a tertiary care hospital in Rwanda

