### **3. Research Questions**

- Is ERAS protocol implementable in Rwanda Tertiary Hospital?
- Is laparoscopic cholecystectomy feasible, safe and cost-effectiveness in the context of ERP in our settings?
- Is possible to discharge laparoscopic cholecystectomy patients within 36 hours postoperative?

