### **4.2. Specific Objectives**

1. To assess the level of knowledge and practice of Health care professional about Enhanced recovery after surgery program.
2. To determine the frequency of postoperative adverse events and complications after laparoscopic cholecystectomy (tress, fatigue, nausea and vomiting)
3. To determine the average length of hospital stay and bed turn over after laparoscopic cholecystectomy
4. To determine the rate and reason of overnight and re-admissions
5. To assess the patients' acceptance of ERAS program and the overall satisfaction
6. To determine the patient cost benefit when ERAS is implemented correctly.

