**5.2.1. Principal measures (elements) contained in the ERP, irrespective of the specialty (32)**

Pre-operative Pre-admission	Intra-operative	Post operative	Post Discharge

1. Patient information and education: Patient optimization (Counseling, smoking, alcohol, pain management plan, pre-habilitation of select patients (e.g., diabetic, hypertensive))
 
2. No bowel preparation
 
3. No premedication
 
4. Initial multimodal medications
 
5. Limited fasting (light meal up to 6 hours preoperative)
 
5. Carbohydrate loading (up to 2 hours preoperative) and Glucose control
 
6. Discharge planning, education and home medication plan
	
1. Limited fluid intake (Normovolemia)
 
2. Normoglycemia
 
3. Corticosteroids
 
4. Prevention of hypothermia (Normothermia)
 
4. Antibiotic prophylaxis
 
6. Prevention of PONV
 
7. Minimal invasive access
 
8. Multimodal analgesia and Limitation of opioid use,
 
8. No drain or nasogastric tube
	
1. Multimodal analgesia
 
2. Katamine , IV lidocaine
 
3. NSAIDs for 48 h
 
4. Nausea and vomiting management
 
5. Early mobilization
 
6. No or judicious IV fluid management
 
7. Early re-feeding
 
8. No or rapid removal of the bladder catheter
 
9. Patient/family education (Delirium prevention)
	
1. Risk management (Monitor for symptoms or changes in health to seek assistance)
 
2. Telephone calls and SMS (Follow-up with surgeon)
 
3. Continue therapy and other activities for recovery as planned

*Source: How to implement an enhanced recovery program? Proposals from the Francophone Group for enhanced recovery after surgery (GRACE):*

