## **6. Expected Results**

Table 1: Level of awareness and knowledge of ERAS among perioperative care health professionals

Table 2: Baseline characteristics of patients

Table 2: Acceptance rate of patients in ERP

Table 3: Rate of adverse events (Stress, fatigue, pain, nausea and Vomiting)

Table 4: Complications of laparoscopic cholecystectomy

Table 5: The average length of hospital stay

Tableau 6: Cost of laparoscopic cholecystectomy

Table 7: Rate of overnight and readmission

Table 8: Overall satisfaction of patients after laparoscopic cholecystectomy in ERP

Table 9: Comparative analysis of length and independents variables

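### Cost data stop at the hospital stay while the objective is the patient's cost benefit, so a saving claimed from them risks being overstated

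*Protocol*

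**What the plan says.** The only rule on cost data is in Section 5.3: "The expenses of surgery and in-hospital care will be calculated and analyzed". The single planned cost output, in Section 6, is "Tableau 6: Cost of laparoscopic cholecystectomy".

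The questions put to these data are broader. Specific objective 6 (Section 4.2) is "To determine the patient cost benefit when ERAS is implemented correctly". The second research question (Section 3) reads "Is laparoscopic cholecystectomy feasible, safe and cost-effectiveness in the context of ERP in our settings". Section 7 uses narrower words, "to increase bed turnover and decrease patients hospital costs".

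The intervention is meant to shorten the stay. Section 2 gives the aim as "decreasing the length of stay from 72 hours to 36 hours". The table in Section 5.2.1 has a post-discharge column that lists "Telephone calls and SMS (Follow-up with surgeon" among its elements. Section 5.2.6 schedules phone follow-up on days 3, 5 and 7, outpatient visits at 15 and 30 days, and at least 48 hours of oral analgesia. Readmission is an outcome (objective 4 in Section 4.2; Table 7 in Section 6), but only as a rate and a reason.

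**The concern.** Cost is measured in the phase where the programme is expected to save, and not in the phase where earlier discharge could add cost. If part of the in-hospital saving returns as drugs, visits, travel or unplanned care that the patient pays for, a figure confined to the hospital stay will look better than the patient's true position. Section 2 gives the point weight, since it motivates the study partly by patients who travel far and have little money.

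This is not a detail that a statistical analysis plan can settle later. It concerns which data are collected. Expenses that nobody asks about by day 30 cannot be recovered at the analysis stage. Cost is also one of six specific objectives and appears in the study title.

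**Working it through.** The Protocol states no cost saving, so there is no figure to reproduce. The check sets the stated scope of the cost data against the stated aims and the scheduled care.

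**Step 1: scope against aim**

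| Item | Where | In the stated cost data? |
|---|---|---|
| Operation and hospital stay | 5.3 | Yes |
| Readmission | 4.2 (objective 4), 6 | Unclear: could be read as in-hospital care |
| Clinic visits, days 15 and 30 | 5.2.6 | No |
| Oral analgesia after discharge | 5.2.6 | No |
| Calls and texts | 5.2.1, 5.2.6, 5.3 | No |
| Travel, unplanned visits | Not mentioned as costs | No |

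The post-discharge contacts in Section 5.3 collect recovery outcomes and patient status. Expenses are not listed.

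**Step 2: is follow-up without cost?** The only post-discharge cost in the Protocol is the communication line in Section 10: 100,000 FRw per month x 6 = 600,000 FRw. Section 5.1 gives 50 to 70 patients.

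- 600,000 / 50 = 12,000 FRw per patient
- 600,000 / 70 = 8,571 FRw per patient

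This is a study expense and not shown as a patient cost. It establishes only that follow-up uses resources outside the hospital stay.

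**Step 3: when would a claimed saving be biased?** Let H be the in-hospital saving against usual care, and E the post-discharge cost under the programme minus that under usual care.

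- Reported saving = H
- Full saving = H - E
- With s = E / H, reported / full = 1 / (1 - s)

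The Protocol gives neither H nor E. Assumed values of s show only how the ratio behaves:

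| s (assumed) | 1 / (1 - s) |
|---|---|
| 0% | 1.00 |
| 10% | 1 / 0.90 = 1.11 |
| 25% | 1 / 0.75 = 1.33 |
| 50% | 1 / 0.50 = 2.00 |

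If follow-up costs the same under both forms of care, E = 0 and there is no bias. If the programme lowers post-discharge cost, E is negative and the in-hospital figure understates the saving. Only the excess over usual care counts. Multiplying an assumed readmission rate by an assumed readmission cost would give a gross omitted amount, which is not this quantity.

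**The case against.** The strongest reply is that the intended claim is about hospital cost and the data match it. Sections 2 and 12 speak of lower cost for the operation and the hospitalisation, and Section 7 speaks of patients' hospital costs. This stands as evidence of one intended scope. It does not cover objective 6 or the cost-effectiveness question, so the Protocol uses two scopes and measures only the narrower one.

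Second, there is at present no saving to overstate. The Protocol has no control arm and no usual-care cost, and its one cost table is descriptive. This stands in full. A reader might infer that the plan necessarily overstates the saving, but the documents do not support that. The risk arises once a saving is claimed against the earlier stay, which objective 6 and Section 7 invite.

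Third, a reader might infer that counting in-hospital cost can only favour the programme. That is also unsupported: the pathway adds resources of its own, such as the multidisciplinary evaluation (Section 5.2.2), carbohydrate loading (Section 5.2.3, on fasting) and blood tests before discharge (Section 5.2.5). In-hospital cost could rise.

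Fourth, the clinic visits may take place under usual care too and cancel out; a readmission may already count as in-hospital care; and recruitment in and near Kigali (Section 5.3) limits travel. All three points stand. They bear on the size of any bias and do not close the gap between objective and measurement.

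**Conclusion.** The mismatch holds: the stated cost data are narrower than objective 6 and the cost-effectiveness question, and they leave out the period into which the pathway moves recovery and follow-up. A saving claimed from in-hospital cost alone risks being overstated. That direction rests on one assumption the Protocol does not establish, namely that post-discharge cost is higher under the programme than under usual care. No size can be given, because neither a comparator cost nor usual follow-up is described; the ratios of 1.00 to 2.00 above illustrate assumed shares and are not estimates. This is a cheap improvement to the data collection and wording, not a demonstrated error in a result.

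**What to change.** Either of two changes resolves the point.

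1. **Widen the data.** At the contacts already planned to day 30, also record what the patient pays for drugs, planned and unplanned visits, and travel. State explicitly that the cost of any readmission to day 30 is counted. Report cost per enrolled patient to day 30, and use the same definition for any usual-care figure. Fix the origin of day 30 at the same time: Section 5.2.6 counts the clinic visits from the operation, whereas Section 5.3 counts its contacts from discharge. A bootstrap confidence interval for the mean would be useful but is optional.
2. **Narrow the claim.** Limit objective 6, the cost-effectiveness question in Section 3 and the conclusion to in-hospital cost, as Section 7 nearly does already.

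The first costs a few extra questions per contact and may give a less favourable cost figure. The second costs only rewording, but gives up the claim about the patient's overall cost.

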### **5.2.5. Postoperative care**

- Analgesia: IV Paracetamol or Katamine administration when necessary.
- No opioids
- Treatment of Nausea and vomiting when necessary

- Pain assessment every 4 hours using pain NRS scale by nursing staff
- If pain not severe: Paracetamol + Ibuprofen or Diclofenac
- Re-feeding
  - Two to 4H after surgery: Liquid diet and mobilization.
  - Withdrawal of intravenous infusions (0.7–1 ml/ kg/h) was obtained during
  - From 8H: light semiliquid meal
  - From the 12H after surgery: a free diet and patient mobilization was further encouraged and increased gradually. All the meals had to be consumed sitting at the table.
- From 24h after surgery: Blood works (FBC and CRP) and Discharge

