#### **5.2.6. Discharge & Post discharge**

The important criteria for the patient's discharge from the hospital are: Normal vital signs and blood works, absence of complications or symptoms, a digestive function enabling the patient to eat without nausea or vomiting, return of intestinal transit with emission of gas (stool not required), autonomy to move and post-operative pain relief with oral analgesics (2).

After the discharge for all the patients, the surgeon will make follow up on phone on day 3, 5 day and day 7 to detect any signs of complications during the first week. If no complaints the out patient clinic evaluation will be planned at 15 and 30 days from the operation. The patient will be given oral analgesia for at least 48 hours.

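### Pain, nausea and vomiting have no common observation window from surgery, so their recorded rates depend on length of stay

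*Protocol*

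**What the plan says.** **Stay.** Section 2 of the protocol gives current practice as "to discharge most patients within two to three days of surgery with a rate of complications around 5" per cent, and states the aim as "decreasing the length of stay from 72 hours to 36 hours". Section 3 asks whether discharge within 36 h of the operation is possible. Section 5.2.5 allows it sooner: "From 24h after surgery: Blood works (FBC and CRP) and Discharge".

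**In hospital.** Section 5.2.5 plans "Pain assessment every 4 hours using pain NRS scale by nursing staff". It gives no assessment interval for nausea or vomiting. The discharge criteria in section 5.2.6 include "absence of complications or symptoms, a digestive function enabling the patient to eat without nausea or vomiting".

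**After discharge.** Section 5.2.6 plans surgeon "follow up on phone on day 3, 5 day and day 7 to detect any signs of complications during the first week", then clinic visits at 15 and 30 days from the operation. Section 5.3 plans patient reports on the Surgical Recovery Scale: "On discharge, on day 3 of discharge, day 10, day 15 and day 30 of discharge patient will report outcomes". It also mentions calls or texts after discharge, with no date and no symptom content.

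**Use of the data.** Specific objective 2 and Table 3 (section 6) report the frequency of these symptoms, with no time window. Section 5.3 also enters pain, nausea and vomiting as predictors of length of stay. Section 7 says that the results will show whether discharge one day after surgery is safe.

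**The concern.** The programme shortens the stay, and scheduled pain scoring takes place only during the stay. Whether early discharge is safe depends largely on what happens in the first hours and days at home. No dated assessment covers that period between discharge and day 3. Two things are at stake.

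- **Table 3.** A patient who leaves at 24 h has less scheduled opportunity to have a symptom recorded than one who stays longer. The rate then mixes symptom frequency with length of observation. It could not be set against the present two-to-three-day practice.
- **The length-of-stay regression.** Longer stays give more chances to record a symptom, and symptoms postpone discharge under the protocol's own criteria. Both push the association in the same direction, whether or not the symptom says anything else about recovery.

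Observations not collected during follow-up cannot be supplied later by any analysis.

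**Working it through.** **Inputs.** Earliest discharge 24 h (5.2.5). Target 36 h (sections 2 and 3). Current discharge 48–72 h (section 2, two to three days). Pain score every 4 h (5.2.5). First dated contact on day 3 (5.2.6 and 5.3), taken here as 72 h after its time origin. The protocol gives no figure for the gap and none for the frequency or timing of these symptoms, so there is no stated result to reproduce.

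**Step 1: gap from discharge at time D to the next dated contact.** From surgery: 72 − D. From discharge: 72 h, reached at D + 72 after surgery.

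| Discharge | Gap, day 3 from surgery | Gap, day 3 from discharge | First contact in the second case |
|---|---|---|---|
| 24 h | 72 − 24 = 48 h | 72 h | 24 + 72 = 96 h after surgery |
| 36 h | 72 − 36 = 36 h | 72 h | 36 + 72 = 108 h after surgery |

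**Step 2: ward hours removed relative to current practice.** Against 48 h: 48 − 36 = 12 h to 48 − 24 = 24 h. Against 72 h: 72 − 36 = 36 h to 72 − 24 = 48 h. The range is 12–48 h.

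**Step 3: scheduled pain scores (hours ÷ 4).** 24 h: 6. 36 h: 9. 48 h: 12. 72 h: 18. These counts show opportunity to record pain under the protocol's own schedule. They are not event rates, and they do not cover nausea or vomiting.

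**Step 4: share of first events recorded before discharge (illustrative).** Let p be the true 0–72 h incidence and H = −ln(1 − p). Let f be the fraction of the 72 h cumulative hazard that has accrued by D. With a constant hazard, f = D/72. With a hazard that halves every h hours, f = (1 − 2^(−D/h)) / (1 − 2^(−72/h)). The rate recorded by discharge is 1 − exp(−H·f), and dividing it by p gives the share captured. Both p and the timing are assumptions. The model also assumes that nothing after discharge is recovered by recall or by an undated call.

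With p = 30%, H = 0.357. Constant hazard, D = 36: f = 0.5, recorded rate 16.3%, share 16.3/30 = 54%.

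| Hazard | Recorded rate, 24 h | Share, 24 h | Recorded rate, 36 h | Share, 36 h |
|---|---|---|---|---|
| Constant | 11.2% | 37% | 16.3% | 54% |
| Half-life 24 h | 18.4% | 61% | 23.2% | 77% |
| Half-life 12 h | 23.8% | 79% | 27.2% | 91% |
| Half-life 6 h | 28.4% | 95% | 29.6% | 99% |

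Across p = 10%, 30% and 50%, the share captured runs from 35% (p = 10%, constant hazard, 24 h) to 99% (half-life 6 h, 36 h). The share missed therefore runs from about 1% to about 65%.

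**Step 5: the regression.** In the constant-hazard row, patients with the same underlying risk record 11.2% if they leave at 24 h, 16.3% at 36 h and 30% at 72 h. An association with stay appears with no difference in risk. With a 6 h half-life the figures are 28.4%, 29.6% and 30%, so this part nearly vanishes. The second part does not depend on timing: a patient with symptoms does not meet the criteria in 5.2.6 and stays longer by rule.

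**The case against.** The strongest reply is that follow-up after discharge is planned. Section 5.3 provides for calls or texts, and the ERP table in section 5.2.1 lists symptom monitoring and telephone or SMS contact. The day-3 report may pick up earlier symptoms by recall, although no recall period is stated. Patients with symptoms should not be discharged, and readmissions are counted. If most events are early and discharge is at 36 h, little is lost. The data-collection checklist, which is not shown, may say more about timing. All of this stands, and it rules out several stronger readings that a reader might reach.

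- *That patients are unmonitored after discharge.* Contacts are planned. What is missing is a date and symptom content before day 3.
- *That the collection window is the stay itself.* The protocol does not limit these events to the inpatient period. Table 3 also lists stress and fatigue, for which 5.2.5 gives no inpatient assessment. The window is simply unstated.
- *That adverse-event rates will fall because patients leave earlier.* The study is one consecutive cohort. No control group is described and no historical rate of pain, nausea or vomiting is given; the figure of about 5% concerns complications. No fall is planned to be estimated.
- *That the two- to threefold difference in pain scores between a 72 h stay and a 36 h or 24 h stay is a bias of that size.* It counts assessments. It also uses only the upper end of two to three days, and it assumes that the 4-hourly schedule would run to 72 h. The 72 h figure may not be wholly postoperative either, since section 2 says patients are now admitted 24 h before surgery.

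A statistical analysis plan could define the window for Table 3. It could not supply assessments that the contact schedule leaves undated.

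**Conclusion.** The point holds in limited form. Pain, nausea and vomiting have no common window from surgery, and no dated assessment lies between discharge and day 3. That interval is 36–48 h or 72 h, depending on a time origin that sections 5.2.6 and 5.3 do not settle between them. Recorded rates therefore depend on length of stay. They may be under-counted just after early discharge, and they would not be comparable with current practice. The regression of length of stay on these symptoms is partly built in.

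The gap follows from the protocol's own times, with day 3 read as 72 h. The size of any under-count is unknown. The range of about 1% to 65% rests on assumed incidence and timing and on no recovery of events after discharge, so it shows only that the protocol's information cannot exclude a material loss. This should be corrected before enrolment, because it bears on objective 2 and on the one-day-discharge conclusion in section 7.

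**What to change.** These changes concern data collection and reporting only.

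1. Define one symptom window for every patient whatever the stay, for example 0–72 h from end of surgery. Report Table 3 on it, split into before and after discharge.
2. Date one of the calls or texts already planned in section 5.3 to the day after discharge. Record pain NRS, nausea, vomiting and unplanned care. At minimum, have the existing day-3 contact ask about each 24 h since discharge.
3. State one time origin for day 3, and reconcile the contact schedules of sections 5.2.6 (days 3, 5 and 7, with clinic at 15 and 30 days from the operation) and 5.3 (days 3, 10, 15 and 30 of discharge).
4. In the length-of-stay regression, use symptoms recorded in a window common to all patients, such as the first 24 h. This removes the unequal opportunity to record. Symptoms that delay discharge by rule will still be associated with stay, and the report should say so.

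**Cost.** One short contact per patient, so 50–70 in all, or no extra contact if the day-3 call is extended. Section 10 budgets follow-up calls as a monthly sum without a cost per contact, so the protocol cannot show that extra calls fit that line. The version without an extra contact carries some recall error, and in either version the recorded rates may look less favourable.
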